To address the gaps in evidence above, we propose a prospective observational study to evaluate the feasibility of beta-lactam TDM in the local setting. Our target population will be adult patients (21 years old and above), admitted to Singapore General Hospital, are receiving beta-lactams for documented or suspected infection and belong to the following group of patients who will most benefit from beta-lactam TDM: i.e. critically ill patients (admitted to intensive care units, intensive care areas, high dependency wards), haematology/oncology patients, burns patients, patients with extracorporeal therapies which will alter beta-lactam pharmacokinetics (e.g. extracorporeal membrane oxygenation, dialysis), patients with resistant infections or deep-seated infections requiring high dose beta-lactam therapy and patients, who are suspected or at risk of developing beta-lactam adverse effects. We will prospectively collect four blood samples over a dosing interval from each patient. The beta-lactam levels will be assayed using liquid chromatography with tandem mass spectrometry. Attending physicians will have the option of knowing the results and whether to accept dose adjustments recommendations by trained infectious disease pharmacist. Proportion of patients attaining therapeutic targets during the first and subsequent TDM will be evaluated. Patients will also be followed up for clinical outcomes such as mortality and clinical response.

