4.2. Criteria for Recruitment and Recruitment Process

Patients, admitted to intensive care units/intensive care areas/high dependency wards/burs department/haematology department/oncology department/renal department/infectious disease department, and are initiated on beta-lactam therapy will be identified from pharmacy dispensing records and screened for eligibility. Physicians may also refer patients to the study team.

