4.3. Inclusion Criteria

- a) Age ≥ 21 years old
- b) Admitted to Singapore General Hospital
- c) Receiving beta-lactams for documented or suspected infection
- d) With indication for beta-lactam TDM: critically ill, altered pharmacokinetics (burns, obese, on extracorporeal therapy e.g. dialysis), immunocompromised (haematology/oncology patients), resistant pathogens, deep-seated infections, suspected

or at risk for adverse effects

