5. STUDY DESIGN AND PROCEDURES/METHODOLOGY

This is a prospective observational study conducted in Singapore General Hospital from October 2019 to September 2020. Patients will be screened for eligibility using criteria 4.3 and 4.4. If women of childbearing age are eligible, the beta HCG result taken during the potential subject's course of hospitalisation will be used to exclude pregnant women. If no beta HCG result is available, clinical case notes will be referred to confirm non-pregnancy status.

Eligible patients will be approached by their treating physicians to seek their consent to be referred to the study team. Informed consent will be taken directly from the patient by the study team once patient is agreeable to be referred to the study team. For subjects who do not have the mental capacity to exercise rational judgement, primary physician will assess and document their mental capacity using the Documentation of Capacity form and substituted consent will be obtained by the study team from the spouse, parent, guardian, or legally acceptable representative of the subject. Consent for continued participation will be obtained from patient directly when he regains mental capacity to give informed consent.

Blood sampling and data collection will only commence once informed consent has been taken. Subjects may withdraw voluntarily from participation in the study at any time. Once they have withdrawn from the study, all subsequent blood sampling and data collection will be discontinued.

All patients will be followed up until end of beta-lactam therapy, 30 days from commencement of beta-lactam therapy, hospital discharge or mortality, whichever occurs later.

Blood sampling:

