For all patients, 4 sets of blood samples (5 mL each) will be obtained via venipuncture or existing cannula access within a dosing interval. We propose to obtain 4 samples for each TDM in this study to generate more robust and accurate drug concentration-time curves for calculation of target attainment and to better characterise patients' pharmacokinetic profiles. For most patients (except those on intermittent extracorporeal therapies), blood samples will be obtained during end of infusion, 1 hour after infusion, 2 hours after infusion and within 30 minutes of the next scheduled dose (i.e. trough level) if beta-lactam is given as short infusion over \leq 30 minutes. If beta-lactam is given as extended infusion (e.g. 3-4 hours), blood samples will be obtained at mid-infusion, end of infusion, 1 hour after infusion and within 30 minutes of the next scheduled dose (i.e. trough level). For patients on intermittent extracorporeal therapies (e.g. intermittent dialysis), blood samples will be obtained at end of beta-lactam infusion, at the beginning of dialysis, end of dialysis and within 30 minutes of the next scheduled dose (i.e. trough level).

To ensure therapeutic targets are reached, further blood sampling, according to the schedule above, may be performed after dose adjustments or when there is a change in patient's clinical status (e.g. change in dialysis settings, change in renal function), which may warrant change in beta-lactam dosing regimen. Blood sampling for TDM will be stopped when beta-lactam has been discontinued, when therapeutic targets are achieved or when patient has been discharged from the hospital.

Assay of beta-lactam levels

All blood samples will be sent to our research laboratory for assay via liquid chromatographytandem mass spectrometry. All blood samples will be labelled by our study team using subject codes (no patient identifiers will be used).

Beta-lactam TDM and Dose Individualisation

The treating physicians will have the option to know the results of the TDM, once available. An infectious disease-trained pharmacist may make recommendations on dose adjustments based on the TDM results. However, accepting these recommendations will be at the discretion of the treating physicians.

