The infectious disease trained pharmacist may use pharmacokinetic software to analyse drug concentration-time profile to guide dose adjustments. If available, dose recommendations will be based on the MIC of the known pathogen, which will be provided by the local microbiology laboratory. Where no pathogen was formally identified, MICs are not available or cultures are pending, the highest MIC (according to the Clinical and Laboratory Standards Institute (CLSI criteria) for susceptible bacteria to the antibiotic will be assumed.

Data Collection

All patients will be followed up from study entry to 30 days from study entry, hospital discharge or mortality, whichever occurs earlier.

Data will be collected from electronic medical records, using a standardised data collection form. These will include:

•patient demographics (unique identifier, age, gender, race, body weight, height, comorbidities including Charlson Comorbidity Index)

•pharmacokinetic-specific data (use of extracorporeal therapy/dialysis and settings, urine output, serum creatinine, albumin)

•clinical data (temperature, blood pressure, heart rate, respiratory rate, mortality, cause of mortality, severity of illness indicators such as APACHE II score and SOFA score, incidence of beta-lactam-related adverse events/side effects as reported by primary physicians, admission and discharge date from hospital and from intensive care unit if applicable)

•laboratory data (albumin, serum creatinine, procalcitonin, CRP, total white count)

•infection-related data (site and type of infection, pathogens isolated and their susceptibility results and reported minimum inhibitory concentrations)

•drug-related data (beta-lactam dosing regimens including any change to dosing regimens, concurrent antibiotic use history and their dosing regimens, presence of any drug which may interact with beta-lactams or interfere with beta-lactam assay results)

•beta-lactam assays levels, attainment of therapeutic targets and whether dose adjustments were made

Data will be stored in a password-protected database and only study team members will have access to data. Identifiers will be stored separately from collected data. Data collection forms will not contain identifiers (e.g. NRIC, name, date of birth). All hardcopy data collection forms and consent forms will be stored under lock and key in the cupboard at [name] of

Pharmacy department in Singapore General Hospital.

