8.2. Statistical and Analytical Plans

Our primary outcome will be attainment of beta-lactam therapeutic targets: 100%fT>MIC, 40-70%fT>5xMIC, 100%fT>5xMIC. Proportion of patients, who achieve beta-lactam therapeutic targets, during the first and subsequent TDM will be determined. For the group of patients, who require dose adjustments, after the 1st TDM and need further TDM, the proportion of patients who require dose increment and dose reduction, the number of TDM performed to achieve therapeutic target and the mean/median time required to achieve therapeutic target will also be evaluated.

Correlation of primary outcomes will be made to the following secondary outcomes.

- a. Mortality at the end of therapy and within 30-day mortality.
- b. Days to defervescence
- c. Days to resolution of white blood cell count, pro-calcitonin and C-reactive protein.

Any incidence of adverse effects related to beta-lactam therapy will also be reported and evaluated in correlation to beta-lactam levels.

For univariate analyses with binomial outcomes (e.g. mortality), Chi-square test or Fisher's exact test will be performed where appropriate. For univariate analyses with time-dependent outcomes (e.g. days to defervescence, days to resolution of inflammatory markers), Kaplan-Meier analysis will be performed. For univariate analyses with continuous outcome variables (e.g. APACHE II score, SOFA score), Student's t-test and Mann-Whitney-U test will be performed for parametric and non-parametric data respectively. Multivariate analyses will then be performed to include potential confounders such as APACHE II score, SOFA score, Charlson comorbidity index, use of beta-lactam as culture-directed therapy, presence of multi-drug resistant infection, and presence of concurrent infections requiring additional antibiotics. Logistic regression will be used for binomial outcomes (mortality) while Cox regression will be used for time-dependent outcomes (days to defervescence, days to resolution of inflammatory markers).

To evaluate population pharmacokinetics in various patient groups, a specialised pharmacokinetic software will be used to develop population pharmacokinetic models. Model simulation will then be performed to design empiric dosing recommendations to guide local practice.

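### Section 8.2 relates beta-lactam levels to adverse effects judged by physicians who may know the level, and does not separate events present at entry from new ones

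*Combined protocol and SAP*

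**What the plan says.** The only planned analysis of toxicity against exposure is one sentence in Section 8.2: "Any incidence of adverse effects related to beta-lactam therapy will also be reported and evaluated in correlation to beta-lactam levels". It gives no event window, no criteria for relatedness, no choice of level (first, last or nearest the event) and no model specific to this question.

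Other sections determine what enters that analysis:

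- **Outcome.** Section 5 (Data Collection) records "incidence of beta-lactam-related adverse events/side effects as reported by primary physicians". No causality scale or independent assessment is described. Section 6.1 defines events resulting from the research, for ethics reporting. It does not supply criteria for relatedness to the antibiotic.
- **Knowledge of exposure.** Section 5 (Beta-lactam TDM and Dose Individualisation) says "The treating physicians will have the option to know the results of the TDM, once available". A pharmacist may recommend a dose change, and the physician decides.
- **Entry.** Section 1 names as a target group "patients, who are suspected or at risk of developing beta-lactam adverse effects". Section 4.3 criterion (d) ends with patients suspected of, "or at risk for adverse effects". Section 4.2 adds "Physicians may also refer patients to the study team".
- **Timing.** Section 5 says "Blood sampling and data collection will only commence once informed consent has been taken", and the Data Collection text starts follow-up at study entry. Nothing says how an event already present at consent is handled.

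The confounders that Section 8.2 gives as examples cover severity, comorbidity and infection. Disclosure of the level and reason for entry are not among them.

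**The concern.** The outcome is a causal judgement, and the person making it may know the exposure. A physician who sees a high level has a reason to call an ambiguous event drug-related, and one who sees an unremarkable level has less reason. The misclassification then depends on exposure, and adjusting for APACHE II, SOFA or comorbidity does not remove it.

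Separately, some patients may enter because an adverse effect is already suspected. If that event is recorded as an outcome, the reported incidence partly reflects how patients were recruited, and the level was drawn after the event it is meant to explain.

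The background section justifies TDM partly by the need to balance efficacy against toxicity at high doses. A level-toxicity result from this study is therefore likely to be read as evidence on that question, even though the plan gives it a small place.

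**Working it through.** **The plan's own figure.** Section 8.1: 40,000/125 = 320 assays, and 320/4 = 80 patients. This reproduces. Repeat TDM is allowed, so 80 is an upper figure: at two sets each it would be 320/8 = 40. The plan gives no rate for adverse effects, attribution or disclosure, so every rate below is an assumption.

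**1. Attribution that depends on the level.** Let e be the true event rate, equal at high and low levels. Let a_H be the chance of attribution when a high level is known, a the chance otherwise, and k the share of high-level patients whose physician has seen the result before attributing.

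Reported rate, high level = e × [k × a_H + (1 − k) × a]. Reported rate, low level = e × a. The ratio does not depend on e. With e = 15%:

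| a_H | a | k | High level | Low level | Ratio |
|---|---|---|---|---|---|
| 0.9 | 0.5 | 1 | 13.5% | 7.5% | 1.80 |
| 0.9 | 0.5 | 0.5 | 10.5% | 7.5% | 1.40 |
| 0.8 | 0.6 | 1 | 12.0% | 9.0% | 1.33 |
| 0.8 | 0.6 | 0.5 | 10.5% | 9.0% | 1.17 |

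If no physician has seen the result (k = 0), the ratio is 1.00. The table lets only a high level shift the judgement. If a known low level also discourages attribution, the distortion grows. With a 10% event rate and attribution of 0.6 (high) against 0.4 (low), the odds ratio is 1.24 when half the physicians view the result and 1.53 when all do. With 0.7 against 0.3 it is 1.53 and 2.43.

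**2. Incidence, if events present at entry are counted.** Let m of 80 patients enter with such an event and 10% of the rest have a new one. The rate is (m + 0.1 × (80 − m))/80:

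- m = 4: 11.6/80 = 14.5%
- m = 8: 15.2/80 = 19%
- m = 16: 22.4/80 = 28%

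**3. Entry because of an event: effect on the association.** Let an existing event lead to entry with probability 0.5, and other indications with probability s. Then S(event) = 1 − (1 − s) × 0.5 and S(no event) = s. The true odds ratio is multiplied by [S(event, high) × S(no event, low)]/[S(no event, high) × S(event, low)]:

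- s equal at 0.3 for both levels: (0.65 × 0.3)/(0.3 × 0.65) = 1.0
- s = 0.5 high, 0.2 low: (0.75 × 0.2)/(0.5 × 0.6) = 0.5
- s = 0.2 high, 0.5 low: (0.6 × 0.5)/(0.2 × 0.75) = 2.0

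Selection on the event alone does not shift the odds ratio. Combined with other entry routes that depend on level, it can shift it either way.

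**4. Dose lowered after an event but before sampling.** Take a 10% risk at low levels, a true odds ratio of 2 (risk at high levels 18.2%) and half the patients at each level. If 20% of high-level patients with an event are then measured as low, the four cells (as fractions of the cohort) are 0.0727 (high, event), 0.4091 (high, none), 0.0682 (low, event) and 0.45 (low, none). The odds ratio is (0.0727 × 0.45)/(0.4091 × 0.0682) = 1.17. With 40% it is 0.69.

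**5. Precision.** With 40 patients per level group, two-sided 5% and a pooled-variance test of two proportions, power is about 24% for 10% against 20%, and 61% for 10% against 30%.

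**The case against.** A reader might infer that the analysis counts the events that led to enrolment and is therefore biased towards showing toxicity. The documents do not support that.

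- **Counting.** No section says an enrolling event is counted. Data collection starts after consent, follow-up starts at study entry, and Sections 5 and 8.2 both speak of incidence. The supportable statement is that such events are not explicitly excluded. The entry criterion also covers patients merely at risk, and the share entering with an actual event is unknown.
- **Direction.** Only level-aware attribution pushes consistently towards toxicity. Selection on the event can leave the odds ratio unchanged or move it either way, and dose reductions before sampling can hide a true effect.
- **Size.** The ratio of 1.8 assumes that every physician of a high-level patient saw the result before attributing the event. Viewing is optional. If half did, the same attribution rates give 1.4.
- **Importance.** Toxicity is not an objective in Section 2 and is not among outcomes (a) to (c) in Section 8.2. The dosing recommendations are to come from pharmacokinetic simulation, and nothing routes this correlation into them.

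All four points stand, and they limit the claim and its severity. They leave one fact untouched: under the plan as written, relatedness may be judged with knowledge of the level, and neither the order of events nor disclosure has to be recorded. The text says primary physicians in one place and treating physicians in the other. I read these as the same clinical team.

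**Conclusion.** The point holds in limited form. The planned correlation is open to attribution that depends on the level, and the handling of events present at entry is unspecified. The first can produce a spurious ratio of about 1.2 to 1.8 under attribution of 80–90% with a known high level against 50–60% otherwise, with half to all physicians viewing the result. Stronger assumptions give more, and no viewing gives none. The second inflates incidence only if those events are counted: from 10% to between 14.5% and 28% for 4 to 16 of 80 patients.

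The net direction of bias in the correlation cannot be determined from the documents. A positive finding would not establish toxicity, and a null finding would not be reassuring. Severity is minor: this is a supplementary analysis in about 80 patients at most, with no power statement. It is worth correcting because the remedy is cheap and the dates are hard to reconstruct afterwards.

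**What to change.** **Add to the existing data collection form:** reason for entry; onset date of each adverse effect; date on which it was attributed to the beta-lactam; whether and when the level was disclosed to the physician. The attribution date is needed as well as onset, because an event that starts before disclosure can still be judged after it.

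**Add to Section 8.2:**

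- Events with onset before the first sample are reported separately and excluded from incidence and from the level correlation.
- The level used is named, for example that of the first TDM, before any TDM-guided dose change. Later dose changes, which the form already captures, are listed alongside.
- The correlation is shown in two strata: attribution made before or without disclosure, and attribution made after it.
- The analysis is labelled exploratory.

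Serum creatinine is already collected and may look like an objective check, but it should not be used to confirm toxicity. Renal function itself affects levels, so the two can be correlated with no drug harm, and creatinine is hard to interpret in dialysis patients.

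**Cost.** A few form fields and a short paragraph in the plan, with no change to patient care. The undisclosed stratum will hold fewer events, perhaps very few, since the time from sample to result is not stated. It is also partly selected by the physicians who chose not to see the result, so the comparison between strata should be read descriptively.

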Current "one-size-fits-all" beta-lactam dosing regimens are largely derived from Phase I clinical studies on healthy volunteers. They may be sub-optimal in clinical practice as patients may display variable and unpredictable pharmacokinetics, for example, those who are critically ill [4,5], febrile neutropaenia [8], burns [28], with renal/liver impairment [29], or require dialysis and other extracorporeal therapies [30]. In fact, studies have shown that conventional beta-lactam dosing recommendations were unable to achieve therapeutic targets in at least 35-50% in these patients [4,5,8,30], requiring further dose adjustments guided by beta-lactam TDM [5,28]. Hence, dose individualisation using TDM is increasingly being advocated.

In addition, technology in dialysis is rapidly evolving with new generation filters, dialysis techniques/modes being developed and placed in clinical practice [31]. However, their effects on beta-lactam disposition and clearance are limited (e.g. limited publication available for plasmapheresis, molecular adsorbent recirculating system therapy). More importantly, in Singapore General Hospital, dialysis filters have now switched from low flux to high flux membranes as the default for most patients. Some studies have reported increased clearance with high flux dialysis for small drug molecules, such as beta-lactams, resulting in reduced antimicrobial exposure with conventional renally-adjusted dosing regimens [32] and potentially affect clinical outcomes. Hence, beta-lactam TDM will be increasingly important in these patients. We would also like to elucidate from this study how these changes in dialysis technology would influence our beta-lactam dosing regimens.

Evidence Gap with Beta-lactam TDM:

Beta-lactam TDM is only performed in a few centres worldwide. Outside Japan, no other Asian countries are reported to perform beta-lactam TDM routinely. As there could be pharmacokinetic/pharmacodynamic differences between Asian and Caucasian populations due to differences in ethnicity, clinical practice (e.g. types and settings of dialyser machines/membranes) and resistance patterns of pathogens, we hope this study could provide early insights to generate recommendations most suitable for our local/Asian population and setting.

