2. HYPOTHESIS AND OBJECTIVES

We hypothesise that current licensed beta-lactam dosing regimens are suboptimal in at least half our patients: patients with severe sepsis in intensive care units/high dependency wards, burns patients, patients requiring dialysis and other forms of extracorporeal therapy, haematology/oncology patients, and patients with resistant pathogens or deep-seated infections requiring high dose beta-lactam therapy. Hence, beta-lactam TDM would be necessary for these patients to optimise their dosing regimens and improve their clinical outcomes.

Our primary objective is to evaluate proportion of sub-optimal beta-lactam levels in correlation to MIC and the need for dose adjustments

Our secondary objectives include:

- 1. Correlating the achieved pharmacokinetic/pharmacodynamic therapeutic targets (100%T>MIC, 40-70%T>5xMIC, 100%T>5xMIC) with clinical outcomes (mortality, clinical response, microbial eradication) in the different sub-groups mentioned above
- 2. Characterising beta-lactam pharmacokinetics (as exploratory analysis) for certain patient populations, with limited beta-lactam pharmacokinetics characterised in primary literature (e.g. those requiring extracorporeal therapy, various types of dialysis), to aid design of empiric dosing regimens suitable for local practice.

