8. SAMPLE SIZE AND STATISTICAL METHODS

8.1. Determination of Sample Size

Patients will be recruited until 320 assays are performed (based on budget of \$40,000, estimated cost of each assay is \$125, number of assays = 40,000/125 = 320 assays). This will be roughly equivalent to 80 patients, assuming patients will have 4 assays each.

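### The mortality model in 8.2 has at most 5.7 events per term at 80 patients, with no fixed covariate set, no small-sample method, and renal function and dialysis unnamed

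*Combined protocol and SAP*

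**What the plan says.** For multivariate analysis, section 8.2 lists "potential confounders such as APACHE II score, SOFA score, Charlson comorbidity index, use of beta-lactam as culture-directed therapy", then multi-drug resistant infection and concurrent infection needing other antibiotics. That is six variables, offered as examples. On method it says "Logistic regression will be used for binomial outcomes (mortality"), with Cox models for time-to-event outcomes. It gives no final covariate set, selection rule, limit on terms or expected number of deaths. Fisher's exact test appears only for univariate comparisons. The exposure has three target definitions, and mortality is counted at end of therapy and at 30 days.

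Section 8.1 derives the size from the budget: "This will be roughly equivalent to 80 patients, assuming patients will have 4 assays each". Section 5 (Blood sampling) adds that "further blood sampling, according to the schedule above, may be performed after dose adjustments", or when clinical status changes. Section 2 hypothesises that "current licensed beta-lactam dosing regimens are suboptimal in at least half our patients".

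On renal function and dialysis:
- Section 1 lists patients "with renal/liver impairment [29], or require dialysis and other extracorporeal therapies" among those with variable pharmacokinetics.
- Section 4.3 makes "altered pharmacokinetics (burns, obese, on extracorporeal therapy e.g. dialysis") an indication for enrolment.
- Section 5 names "change in dialysis settings, change in renal function), which may warrant change in beta-lactam dosing regimen".
- Section 5 (Data Collection) records serum creatinine, urine output and dialysis settings, without collection times.
- Section 8.2 mentions none of these.

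**The concern.** A logistic model with seven or more terms and few deaths is a poor setting for ordinary ML. Estimates drift away from the null and become noisy. If a combination of covariates predicts death perfectly (separation), there is no finite estimate. With an open covariate list, three targets and two mortality time points (3 x 2 = 6 attainment-mortality models), the model could also be chosen after the results are known.

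Renal function and dialysis matter because the protocol itself treats them as drivers of exposure. If they also relate to mortality by a route other than drug exposure, leaving them out confounds the attainment effect.

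The stake is the aim in section 1 of finding which target is best for practice. These estimates feed that choice. Section 2 marks the pharmacokinetic objective as exploratory but does not mark the target-outcome objective that way.

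**Working it through.** **Plan's own figure.** 40,000/125 = 320 assays; 320/4 = 80 patients. Reproduced. It assumes one four-sample set per patient, so no repeat TDM.

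**Terms.** Six named confounders + one attainment term = 7, with one term per variable and one target per model.

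**Ceiling on events per term.** The smaller outcome class is at most N/2, so the ceiling is (N/2)/7. If a fraction r of patients has one repeat set (r is assumed), N = 320/(4(1 + r)).

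| r | N | Ceiling, 7 terms | Ceiling, 9 terms |
|---|---|---|---|
| 0 | 80 | 40/7 = 5.7 | 40/9 = 4.4 |
| 0.25 | 64 | 32/7 = 4.6 | 32/9 = 3.6 |
| 0.5 | 53 | 26.7/7 = 3.8 | 26.7/9 = 3.0 |

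**At assumed mortality of 10-30%.** Deaths per term = N x mortality/7. For N = 80: 8/7 = 1.1 to 24/7 = 3.4. For N = 53: 5.3/7 = 0.8 to 16/7 = 2.3.

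**Simulation.** All inputs are assumed. There were 3,000 datasets per cell, with a true attainment OR of 0.50, attainment in 50% and independent of covariates, and an APACHE II-SOFA correlation of 0.7. Mortality log ORs were 0.4 per SD for each severity score, 0.3 per SD for Charlson, -0.2 for culture-directed therapy (50%), 0.5 for resistance (30%) and 0.3 for concurrent infection (30%). Creatinine and dialysis (25%) had no effect on mortality, so the run shows only the cost of adding them. ML used the seven terms and is summarised on non-separated datasets only. Firth in this table used eight terms, with creatinine and dialysis added and SOFA left out, on all datasets. Cells show average OR (RMSE of log OR).

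| N | Mortality | ML | ML separates | Firth |
|---|---|---|---|---|
| 80 | 10% | 0.40 (1.66) | 17% | 0.50 (0.93) |
| 80 | 20% | 0.44 (0.85) | 0.8% | 0.50 (0.69) |
| 80 | 30% | 0.45 (0.69) | 0% | 0.50 (0.58) |
| 53 | 10% | 0.38 (2.09) | 41% | 0.52 (1.14) |
| 53 | 20% | 0.40 (1.48) | 7.3% | 0.50 (0.98) |
| 53 | 30% | 0.41 (1.08) | 0.7% | 0.49 (0.80) |

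On the same non-separated datasets at N = 80, Firth gives 0.53/0.51/0.50 (RMSE 0.80/0.68/0.58), so its advantage does not come from the choice of datasets. The ML average at 10% mortality is unstable because of near-separated fits.

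**Size of the ML bias.** At N = 80 and 20% mortality: ln(0.438/0.5) = -0.13; against an SD of 0.84 that is 0.13/0.84, about 0.16 SD.

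**Keeping or dropping SOFA (N = 80; mortality 10/20/30%).** With attainment independent of covariates, Firth on the plan's own seven terms gives 0.50/0.49/0.50 (RMSE 0.97/0.67/0.58), much as in the table. If attainment depends on SOFA (assumed log OR -0.6 per SD), Firth without SOFA gives 0.47/0.45/0.44 in one run and 0.45/0.44/0.44 in another. Firth on nine terms, with SOFA kept and creatinine and dialysis added, gives 0.50/0.49/0.48.

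**Precision.** At N = 80 the eight-term Firth model detects a true OR of 0.50 in 11/18/23% of datasets. When the true OR is 1, 39/25/21% of its estimates fall outside 0.5-2 (ML 50/33/27%).

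**The case against.** The best reply is that this is a secondary analysis in a budget-sized observational feasibility study, that the ML bias is small beside the noise, and that Firth neither raises events per term nor makes the estimates precise. All of that is true. What remains is that Firth had lower error than ML in every cell, always gives a finite estimate, and costs only wording.

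On renal function and dialysis, a reader might infer that the plan excludes them or that confounding is certain. The documents support neither. The list is open, and section 2 plans the outcome correlation within sub-groups that include dialysis patients, although 8.2 never puts that into an analysis. A confounder must also affect mortality. Section 1 suggests dialysis could affect outcomes, but through reduced drug exposure, which does not by itself make it a confounder.

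A reader might also conclude that SOFA should go because it overlaps with APACHE II. The documents call both severity indicators and say nothing about their correlation. Dropping SOFA brought no visible precision gain at 20-30% mortality, and it brings bias back if attainment depends on SOFA.

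Finally, 53 patients is not a forecast. Suboptimal dosing in half of patients does not mean that half will be resampled, because repeat sampling is optional and dose changes are left to the treating physician.

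**Conclusion.** The point holds as one of prespecification and method for a secondary analysis. The ceiling of 5.7 events per term at 80 patients follows from the plan's own figures whatever the death rate, given seven terms. Reading the planned model as ordinary ML is an inference from the absence of any other named method.

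The rest depends on assumed mortality, effect sizes and repeat fractions: exaggeration of about 0.16 SD at 20% mortality, higher RMSE than Firth, and separation at 10% mortality in about 17% of datasets with N = 80 and about 40% with N = 53. Omitting renal function and dialysis may leave residual confounding; its size and direction cannot be derived from the documents.

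Two further inferences go too far. Firth does not make these data adequate for choosing an optimal target, as the detection rates show. The Cox models were not simulated, so nothing is claimed about their covariate set. The primary attainment proportions are unaffected.

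**What to change.** In 8.2, state that mortality is analysed by Firth-penalised logistic regression with profile-likelihood 95% confidence intervals, one target definition per model, with nine prespecified single terms:
- target attainment at first TDM, as the exposure in this model;
- all six confounders already named, including SOFA;
- serum creatinine at or closest to first TDM;
- an indicator for dialysis or other extracorporeal therapy at first TDM.

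Label the target-outcome associations as exploratory in sections 2 and 8.2. In section 5 (Data Collection), fix the timing of creatinine and dialysis status; the severity scores have no stated time either, and one can be set in the same line.

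The cost is wording only, with no extra blood samples, assays or patients. The downsides are slight shrinkage towards the null, one indicator that pools different extracorporeal therapies, and two more terms (ceiling 40/9 = 4.4), which in simulation cost little or no RMSE at N = 80. Estimates stay imprecise, which is why the exploratory label is part of the fix.
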